9.1. Covariate adjustment

In the first instance, intervention effects between groups for all outcomes will be adjusted for the baseline score (where appropriate), minimisation parameters (Gender, baseline EHRA) as well as age at randomisation and

baseline LVEF (as continuous variables). The minimisation variable EHRA is a categorical score with the following categories (1, 2a, 2b, 3, 4) and for minimisation, this score was categorised into (class 1, 2a) and (class 2b, 3, 4). However for the analysis we will be adjusting this variable in its original 5 categorical form.

The Bisoprolol arm will be used as a reference category for all model based analyses.

For some binary outcomes, sometimes the effect size to be estimated of interest is the relative risk rather than the odds ratio and so for these outcomes, a log-binomial model is often used. However there are convergence issues with this type of model and so if the log-binomial model fails to converge, a Poisson regression model with robust standard errors will be used to estimate the same parameters.⁷ If this also fails to converge, unadjusted estimates will be produced from the log-binomial model. It will be made clear in the final report why this occurred (e.g. not possible due to low event rate/lack of model convergence).

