- General Health Perception Score = ((GHP-5)/20)*100

AGPHYSICO

$(PF*0.456) + (RP*0.362) + (Pa*0.367) + (GHP*0.199) + (EV*-0.050) + (SF*-0.028) + (RE*-0.110) + (MH*-0.256)$

AGMENTCO

$(PF*-0.227) + (RP*-0.102) + (P*-0.130) + (GHP*0.036) + (EV*0.278) + (SF*0.272) + (RE*0.329) + (MH*0.460)$

Physical Component Summary score (PCS)

$((AGPHYSICO-82.261)/20.867)*10+50$

Mental Component Summary score (MCS)

$((\text{AGMENTCO}-63.7796)/19.582)*10)+50$

EQ-5D (5 level)

The current NICE guidelines (updated October 2019) on the use of EQ-5D-5L scoring based on the most recent value set for England published by Devlin et al. 2018 was not to use this and instead to map the 5L data into 3L value set based on mapping function developed by van Hout et al. 2012.

EQ-5D-5L have developed the crosswalk value sets for the 5L to 3L and so these values will be used for scoring: (<https://euroqol.org/eq-5d-instruments/eq-5d-5l-about/valuation-standard-value-sets/crosswalk-index-value-calculator/>).

For those patients that die prior to completing the EQ5D questionnaire, for the Index score a value of "0" will be imputed since for this questionnaire, a value of 0=death.

AFEQT questionnaire overall score

$$100 - \left[\frac{(\text{sum of severity for all questions answered} - \text{number of questions answered}) * 100}{\text{Total number of questions answered} * 6} \right]$$

*Note: ignore last two questions of the AFEQT questionnaire for scoring as they will be tabulated separately

IPAQ score (as continuous score)

- Sitting = N/A for IPAQ score
- Walking = 3.3 METs
- Moderate Intensity = 4.0 METs
- Vigorous Intensity = 8.0 METs

Total MET-minutes/week: MET level x minutes of activity/day x days per week

IPAQ score= Walk (3.3*min/day*days) + Moderate (4.0*min/day*days) + Vigorous (8.0*min/day*days)

NT-pro-BNP

Since this data is expected to be not normally distributed, a log transformation (natural log) for this data will need to be done to approximate normality prior to any analysis.

Composite of diastolic indices

This outcome will be coded as a binary yes/no, with "yes" representing patients that have a diastolic dysfunction present and "no" for patients that don't.

There is an algorithm to determine whether the patient has a diastolic function or not and it will be computed based on the following:

Does the patient have any **one** of the following diastolic parameters?

- Average E/e' (taken from lateral and septal wall) ≥ 15

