9.6. Analysis methods – secondary outcomes

A template for reporting all the secondary outcomes is given in Appendix D6.

Patient-reported QoL

For the RATE-AF trial, questionnaires SF-36v2, EQ-5D-5L and AFEQT are administered at baseline, 6 months and 12 months.

Up-titration visits:

These questionnaires are also administered for each patient at their last up-titration visit.

Note: the data for last up-titration visit is not done at any scheduled time-point due to the fact that each patient will have different up-titration visits (i.e. some will have 6 and some may only have 1) and so for this reason the data collected for last up-titration visit will only be summarised by treatment arm and no formal analysis for this data will be conducted.

- **SF-36v2 global and domain specific scores at 6 and 12 months**

The data for these outcomes are continuous in nature and the computation for the global and domain specific scores is described in the data manipulations section 9.4. The mean and standard deviation along with minimum and maximum values for global and domain specific scores will be presented by treatment arm and time-point.

The global and domain-specific scores will be analysed separately at 6 and 12 months using the same analysis methods as described in section 9.5. for primary outcome:

- Physical component summary (PCS) score at 12 months
- Mental component summary (MCS) score at 6 months and 12 months
- Physical Function score at 6 months and 12 months

- Role Limitation Due to Physical Problems score at 6 months and 12 months
- Role Limitation Due to Emotional Problems score at 6 months and 12 months
- Social Functioning score at 6 months and 12 months
- Mental Health score at 6 months and 12 months
- Energy/Vitality score at 6 months and 12 months
- Pain score at 6 months and 12 months
- General Health Perception score at 6 months and 12 months

The range for each domain of the SF-36v2 is from 0=worst score to 100=best score. The Bisoprolol arm will again be used as a reference category for all model based analysis for SF-36v2 and so higher values will indicate better outcome for Digoxin arm.

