The range for AFEQT overall score is from 0=complete disability to 100=no disability. The Bisoprolol arm will again be used as a reference category for the model based analysis of this and so higher values will indicate better outcome for Digoxin arm.

Cardiac function

- **Echocardiographic LVEF at 12 months**

The data for this outcome is a continuous score (presented as a percentage of volume ejected) and is also categorised using the following categories; "<40%", "40-49%", "≥50%". This data is collected at baseline and at

12 months. This data will be summarised as the mean, standard deviation, minimum and maximum values for the continuous score as well as number and percentage for the categories by treatment arm and time-point.

The main analysis of this data will be based on the continuous data so this outcome will be analysed using the same analysis methods as described in section 9.5 for primary outcome. For this outcome only, additional covariates for history of myocardial infarction (MI) at baseline, coronary angioplasty or stents (PCI) at baseline and coronary artery bypass surgery (CABG) at baseline will also be adjusted for in the model. Higher values of LVEF are considered better and since the Bisoprolol arm will again be used as a reference category for the model based analysis of this, higher values will indicate better outcome for Digoxin arm.

- **Diastolic function (E/e' and composite of diastolic indices) at 12 months**

The data for E/e' is a ratio and so continuous in nature. This data is collected at baseline and at 12 months. The mean and standard deviation along with minimum and maximum values will be presented by treatment arm and time-point.

This outcome will be analysed using the same analysis methods as described in section 9.5 for primary outcome. Lower values of E/e' are considered better and since the Bisoprolol arm will again be used as a reference category for the model based analysis of this, lower values will indicate better outcome for Digoxin arm.

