The data for the composite of diastolic indices is a binary (yes/no) and will be computed as described in the data manipulations section 9.4. This data is collected at baseline and 12 months and will be summarised as number and percentage by treatment arm and time-point. The analysis for this outcome will be conducted using a logistic regression model, where the outcome will be the binary category (yes/no) at 12 months and independent variables in the model being the baseline category, treatment arm, all minimisation variables, age at randomisation and baseline LVEF. An adjusted odds ratio and 95% confidence interval will be estimated from the logistic regression model.

- **Change in heart rate**

The data type for heart rate is continuous in nature. This data is collected at baseline, 6 months and at 12 months. The mean and standard deviation along with minimum and maximum values will be presented by treatment arm and time-point for 1) Radial heart rate, 2) Apical heart rate, 3) 12-lead ECG heart rate, and 4) 24-hour ambulatory average heart rate. The 24-hour ambulatory heart rate is only measured once and so no baseline score will be there to adjust for it in analysis.

These outcomes will be analysed using the same analysis methods as described in section 9.5 for primary outcome and analysis will be done separately for 6 and 12 month time-points.

A scatter plot of radial vs apical heart rate at each time point will be produced to visualise the radial-apical discrepancy.

Functional assessment

- **Six-minute walking distance at 6 and 12 months**

The data for this outcome is continuous in nature and this test is conducted at baseline, 6 months and 12 months. The time (measured in min/s) and distance (measured in metres) are only recorded if the patient did the test. Therefore this data will be summarised by treatment arm and time-point with respect to the number of patients conducting the test, the mean and standard deviation, median and IQR as well as minimum and maximum values for time and distance covered. Reasons for stopping the test prematurely were also collected and so this will also be summarised by treatment arm and time-point.

The main endpoint for this outcome is the distance (in metres) walked and so this will be analysed using the same analysis methods as described in section 9.5 for primary outcome and analysis will be done separately for 6 and 12 month time-point.

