- **Change in European Heart Rhythm Association (EHRA) class at 6 and 12 months**

The data for this outcome is categorical in nature and in 5 orderly categories; 1=None, 2a=Mild, 2b=Moderate, 3=Severe, 4=Disabling. This data is collected as baseline, 6 months and 12 months. This data will be summarised as number and percentage by treatment arm and time-point with respect to the EHRA class.

The analysis for this outcome will be conducted using an ordinal logistic regression model, where the outcome will be the EHRA class at follow up (with EHRA class 1 being the reference category) and independent variables in the model being the baseline EHRA class, treatment arm, gender, age at randomisation and baseline LVEF. An adjusted odds ratio and 95% confidence interval will be estimated from the ordinal logistic regression.

Higher EHRA class is considered to be a worse outcome and since the Bisoprolol arm will be used as a reference category in the model, higher values will indicate worse outcome for Digoxin arm.

Note: separate analysis will be done for 6 month and 12 month time-point.

We will also code this outcome as a binary “yes/no” variable where “yes” will be determined if patients had a 2 class improvement in the EHRA class from baseline. The full details for the computation of this are described in the data manipulations section 9.4.

The analysis for this outcome will be conducted using a logistic regression model, where the outcome will be the computed binary variable “yes/no” (with yes being the reference category) and independent variables in the model being treatment arm, gender, age at randomisation and baseline LVEF. An adjusted odds ratio and 95% confidence interval will be estimated from the logistic regression model.

Since we are modelling whether patients had an improvement from baseline and that the Bisoprolol arm will be used as a reference category in the model, higher values will indicate better outcome for Digoxin arm.

Note: again separate analysis will be done for 6 month and 12 month time-point.

Biomarkers

- **Change in NTpro-B-type natriuretic peptide (NTpro-BNP) levels**

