Reference group for the treatment arm in the model is Bisoprolol arm

Higher values indicate better scores so a positive mean difference favours Digoxin arm

Diastolic function	Time point	Statistic	Digoxin	Bisoprolol	Logistic regression model	
					Adjusted Odds Ratio ¹ 95% CI	P-value ¹
Composite of diastolic indices	Baseline	No			-	-
		Yes				
	No					
	Yes					
		No				
		Yes				
Composite of diastolic indices	12 months	No				
		Yes				
	No					
	Yes					
		No				
		Yes				

1-Adjusted for treatment arm, baseline score, all minimisation variables, age at randomisation and baseline LVEF

Reference group for the treatment arm in the model is Bisoprolol arm

Higher values indicate better scores so an odds ratio >1 favours Digoxin arm

Change in heart rate

Secondary outcome	Time point	Statistic	Digoxin	Bisoprolol	Linear regression model	
					Adjusted mean difference ¹ 95% CI	P-value ¹
Radial Heart (bpm)						
Radial Heart rate (bpm)	Baseline	N Mean [SD] Min - Max			-	-
	6 months	N Mean [SD] Min - Max				
	12 months	N Mean [SD] Min - Max				
Apical Heart rate (bpm)						
Apical Heart rate (bpm)	Baseline	N Mean [SD] Min - Max			-	-
	6 months	N Mean [SD] Min - Max				
	12 months	N Mean [SD] Min - Max				
12-lead ECG Heart rate (bpm)						
12-lead ECG Heart rate (bpm)	Baseline	N Mean [SD] Min - Max			-	-
	6 months	N Mean [SD] Min - Max				
	12 months	N Mean [SD] Min - Max				
24-hour ambulatory average Heart rate (bpm)						
24-hour ambulatory Heart rate	24-hour	N Mean [SD] Min - Max				

¹-Adjusted for treatment arm, baseline score, all minimisation variables, age at randomisation and baseline LVEF

The Bisoprolol arm will be used as a reference category

Six-minute walking distance at 6 and 12 months

Six-minute walking test	Digoxin (N=)	Bisoprolol (N=)	Total (N=)
6 months follow-up			
Did the patient undergo the 6-min walk test? No Yes Missing			
If yes: Total time spent (min/s) Median {IQR} Min - Max Total distance covered (m) Median {IQR} Min - Max Was the test stopped prematurely? No Yes			
12 months follow-up			
Did the patient undergo the 6-min walk test? No Yes Missing			
If yes: Total time spent (min/s) Mean [SD] Median {IQR} Min - Max Total distance covered (m) Mean [SD] Median {IQR} Min - Max Was the test stopped prematurely? No Yes			

Distance covered (in metres) from the 6-minute walk test

Secondary outcome	Time point	Statistic	Digoxin	Bisoprolol	Linear regression model	

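### Both diastolic-function footnotes in SAP Appendix D6 state the direction of benefit the wrong way round, and one phrase on two-class EHRA improvement in SAP 9.6 conflicts with the text around it

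*SAP*

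**What the plan says.** SAP 9.1 sets the direction of every comparison: "The Bisoprolol arm will be used as a reference category for all model based analyses". Each mean difference is therefore digoxin minus bisoprolol, and each ratio is digoxin over bisoprolol. SAP 9.6 then points to the results shells: "A template for reporting all the secondary outcomes is given in Appendix D6".

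- **E/e'.** SAP 9.6 treats lower values as better and says that "lower values will indicate better outcome for Digoxin arm". The footnote to the E/e' table in Appendix D6 says "Higher values indicate better scores so a positive mean difference favours Digoxin arm".
- **Composite of diastolic indices.** SAP 9.4 makes this a binary variable, with *yes* "representing patients that have a diastolic dysfunction present". SAP 9.6 specifies a logistic model "where the outcome will be the binary category (yes/no) at 12 months" and an adjusted odds ratio, but gives no direction of benefit. The D6 footnote says "Higher values indicate better scores so an odds ratio >1 favours Digoxin arm".
- **Two-class EHRA improvement.** *Yes* means improved. SAP 9.6 describes the logistic outcome "with yes being the reference category", then says that improvement is what is being modelled and that higher values are better for digoxin. The D6 footnote for this table agrees with that later statement.

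**The concern.** The footnotes in D6 are the SAP's prespecified rule for reading each result. E/e' and the composite together make up the whole diastolic-function secondary outcome, so both halves carry a reversed rule. If the shells are filled in and the footnotes kept, a digoxin benefit on diastolic function would be labelled as favouring bisoprolol, and a harm would be labelled as a benefit.

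The EHRA phrase is a different kind of problem. There the footnote is right, but the modelling instruction could lead a programmer to fit the complementary event. The estimate itself would then be inverted, not only its label.

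**Working it through.** **1. Count of direction footnotes in D6.** The tables that state a direction are SF-36, EQ-5D-5L, AFEQT, LVEF, E/e', the diastolic composite, walk distance, ordinal EHRA, two-class EHRA improvement and NTproBNP. That makes 10; the heart-rate table states none. Each was compared with the outcome coding in 9.4 and the model text in 9.6, or with the natural direction of the scale. Eight are right. E/e' and the composite are wrong.

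**2. E/e'.** The two statements in 9.6 and D6 cannot both hold. The algorithm in 9.4 settles which is wrong: an average E/e' of 15 or more is enough by itself to define dysfunction, and a value of 11 or more counts as one of the adverse parameters in the second step. High E/e' is therefore adverse, 9.6 is right and the footnote is wrong.

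Illustration with assumed means of 11 on digoxin and 13 on bisoprolol: difference = 11 − 13 = −2. This is a digoxin benefit, but under the D6 rule it reads as favouring bisoprolol.

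**3. Composite.** With *yes* (dysfunction) as the event and bisoprolol as reference:

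OR = [p_dig / (1 − p_dig)] / [p_bis / (1 − p_bis)]

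The documents give no dysfunction rates, so those below are assumptions. With 50% on bisoprolol the denominator is 0.50/0.50 = 1.

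| Assumed dysfunction, digoxin | Odds ratio | Arm with less dysfunction | Arm favoured under the D6 rule |
|---|---|---|---|
| 30% | 0.30/0.70 = 0.43 | digoxin | bisoprolol |
| 35% | 0.35/0.65 = 0.54 | digoxin | bisoprolol |
| 45% | 0.45/0.55 = 0.82 | digoxin | bisoprolol |

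As a check, an unadjusted logistic model was fitted to constructed data: 72 per arm (half of the 144 in the power calculation) with assumed dysfunction of 25% on digoxin and 50% on bisoprolol. It gave an odds ratio of 0.33 with *yes* as the event and 3.0 with *no* as the event. The footnote is correct only under the second coding, which the SAP does not specify.

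**4. Two-class EHRA improvement.** Assumed improvement is 50% on digoxin and 35% on bisoprolol.

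- *Yes* as the event: (0.50/0.50) / (0.35/0.65) = 1.86, which favours digoxin and agrees with both 9.6 and D6.
- *Yes* as the base level, so that *no* is the event: 1/1.86 = 0.54, which the D6 rule would read as favouring bisoprolol.

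The parenthesis is the outlier, because the sentences after it and the footnote agree with each other. It is still not safe to ignore: the ordinal EHRA model in the same part of 9.6 uses the term *reference category* for its lowest class, that is, for a base level.

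**The case against.** The best counter-argument concerns the composite. SAP 9.6 does not name the modelled event, so the footnote is not strictly contradicted: if absence of dysfunction were modelled, an odds ratio above 1 would favour digoxin. The EHRA parenthesis, carried over to the composite, would even produce that coding. This stands to the extent that the error depends on the coding, and the correction must name the event. It does not rescue the footnote. *Yes* is defined as dysfunction, modelling *yes* is the ordinary reading of a yes/no outcome, and nothing in the SAP says otherwise.

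It can also be said that 9.6 already settles E/e', that D6 is an empty shell to be completed by a qualified statistician, and that arm-level means and counts sit in the same tables. All of this is true and limits the harm: a careful reader would notice. But D6 is where the SAP places its interpretation rules, and for the composite it is the only place that gives a direction. Nor are the footnotes a uniform convention. Those for ordinal EHRA and NTproBNP correctly reverse the direction where lower is better. The E/e' footnote has the same wording as the LVEF one, and the composite footnote the same as the two-class EHRA one, which suggests text carried over from outcomes where higher is better.

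On EHRA, the direction is stated correctly in two places and the parenthesis is probably loose wording. That is accepted; it is a wording correction and is not counted among the wrong footnotes.

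**Conclusion.** The point holds. Two of the ten direction footnotes in D6 are wrong. The E/e' footnote contradicts 9.6 and the dysfunction algorithm in 9.4. The composite footnote is reversed under the ordinary coding, with *yes* as the event, and no direction statement elsewhere corrects it. The phrase on two-class EHRA improvement conflicts with the text around it and would invert the odds ratio only if coded literally.

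For E/e' and the composite the consequence is a wrong label: estimates, confidence intervals and p-values are unaffected. The primary outcome and the sample size are not touched. The rates and means used above are assumptions that show direction only; they do not predict the size of any effect in this trial. The correction should be made before the tables are produced, because following D6 as written would credit both diastolic-function results to the wrong arm.

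**What to change.** - **E/e' footnote in D6:** state that lower values are better and that a negative mean difference favours digoxin.
- **Composite:** state in 9.6 that the modelled event is *yes*, dysfunction present. In the D6 footnote, state that an odds ratio below 1 favours digoxin.
- **Two-class EHRA improvement in 9.6:** replace the parenthesis with a statement that *yes* (improved) is the modelled event and *no* is the reference category. Leave the D6 footnote for this table as it is.

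The cost is two footnotes and two phrases. Data, models and sample size do not change.

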Appendix D7: Feasibility outcomes

Recruitment target of 3 patients per week across all participating centres

To be presented graphically

Compliance and reasons for non-compliance

See section Appendix D3

Number of withdrawals and losses to follow-up (with reasons)

Drop-outs	Digoxin (N=)	Bisoprolol (N=)	Total (N=)
Lost to follow-up			
Withdrawn			
Death			
Total			

List of reason for withdrawals – Digoxin

- 1)
- 2)
- 3)
- ...

List of reason for withdrawals – Bisoprolol

- 1)
- 2)
- 3)
- ...

List of reason for death – Digoxin

- 1)
- 2)
- 3)
- ...

List of reason for death – Bisoprolol

- 1)
- 2)
- 3)
- ...

Drug discontinuation rate and adverse reactions requiring drug discontinuation

Has patient stopped medication due to AE's?	Digoxin (N=)	Bisoprolol (N=)	Total (N=)
No			
Yes			
Missing			
If yes, was it stopped:			
Temporarily			
Permanently			

Cardiovascular Events (from the cardiovascular event form and as identified from the SAE form)

- List of all cardiovascular related events

Number of patients needing therapy-induced requirement for additional treatment

Therapy-induced requirement	Digoxin (N=)	Bisoprolol (N=)	Total (N=)
6 months follow-up			
Did the patient have a pacemaker fitted? No Yes Missing			
If yes: Type of pacemaker Single chamber Dual chamber			
12 months follow-up			
Did the patient have a pacemaker fitted? No Yes Missing			
If yes: Type of pacemaker Single chamber Dual chamber			

Population-specific standard deviations (SD) and proportions

Outcome	6 months			12 months		
	Digoxin	Bisoprolol	Total	Digoxin	Bisoprolol	Total
SF36 PCS N - [SD]						
SF36 MCS N - [SD]						
AFEQT N - [SD]						
LVEF N - [SD]						
E/e' N - [SD]						

Unplanned hospitalisation rates (as recorded from the SAE form)

Unplanned hospitalisation rates	Digoxin (N=)	Bisoprolol (N=)	Total (N=)
No of patients exactly with: 1 unplanned hospitalisation 2 unplanned hospitalisation ... unplanned hospitalisation			
Total number of unplanned hospitalisation			

